9.6 Efficacy Subgroup Analysis

To determine if the following factors have an impact on the response to treatment, subgroup analyses will be conducted on the change from baseline to final visit on the NMSS total score and PDSS-2 total score:

- Gender
- Age category (< 65 , ≥ 65)
- Duration of Parkinson's disease (< 10 years, ≥ 10 years)
- Total daily dose of levodopa (< 1250 mg, ≥ 1250 mg) at the end of initial LCIG titration for the LCIG group and in the first set of dosing diary for the OMT group
- Number of anti-PD medications other than levodopa taken at any time during the week prior to randomization (0 or 1, 2 or more)

The subgroup analyses will be performed using an ANCOVA model contain treatment, country, and subgroup as main effects, treatment by subgroup interaction, and baseline score as the covariate. The LS mean change for each stratum of the subgroup with associated 95% confidence interval will be presented.

The descriptive statistic summary described for the NMSS and PDSS-2 total scores will also be prepared for each subgroup stratum.

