In accordance with the LCIG approved Product Label for countries participating in the study, those subjects randomized to LCIG must discontinue all other anti-PD medications (e.g., dopamine agonists, COMT-inhibitors, amantadine, MAO-B inhibitors, anti-cholinergics, and subcutaneous apomorphine etc.) prior to LCIG initiation on Day 1 (V4); these medications should be tapered off according to the prescribing information and the discretion of the Investigator. With the exception of continuous subcutaneous delivery of apomorphine or levodopa containing formulations, these medications may be restarted if indicated by the subject's individual condition, but not within the first 28 days after LCIG initiation.

For those subjects randomized to LCIG, an optional, temporary nasojejunal (NJ) tube may be used initially to titrate the dose of LCIG. Following the NJ phase, a percutaneous endoscopic gastrostomy with a jejunal tube (PEG-J) will be performed by a gastroenterologist proceduralist. Total time to titration via the NJ and PEG-J should not exceed 14 days. Alternatively, subjects may proceed directly to placement of the permanent PEG-J tube without the NJ phase at the discretion of the principal investigator. If the subject proceeds directly to PEG-J, titration should be completed within 7 days. However, at the PI's discretion additional days of optimization may be made if indicated. Subjects on LCIG will return for study visits at the end of Weeks 2, 6, 12, 26 and 27 following PEG-J placement.

Methodology (Continued):

LCIG Group (Continued):

Subjects and/or caregivers must come into the clinic or pharmacy between V7 (Week 12) and V8 (Week 26) for clinical LCIG return and supply visits so that there is no risk of medication expiring. The drug dispensing visits will occur at Weeks 17 and 22 (\pm 7 days). Other assessments may be completed during these visits if required.

During the treatment phase, medications used to treat specific non-motor symptoms must remain stable for the duration of the study unless medically warranted.

Study Follow-Up

The OMT subjects will not have a follow-up visit (V9).

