8.6 Total Daily Levodopa Dose

For all randomized subjects, the total daily levodopa dose on the day prior to Visit 1 and on the day of randomization will be considered the subject's screening and baseline levodopa dose, respectively. Following Screening Visit 3, subjects randomized to the LCIG group will have NJ/PEG-J placement and discontinue all anti-PD medications other than levodopa-carbidopa that will be continued during LCIG treatment as post-infusion nighttime therapy. Subjects in the LCIG group are to record all LCIG infusions during the 3 days before each scheduled study visit on a Subject Dosing Diary. Subjects in the OMT group are to record all anti-parkinsonian medications taken during the 26-treatment period on the Subject Dosing Diary.

For each Subject Dosing Diary, the overall total daily dose of levodopa will be determined for each subject in the Safety Dataset, as well as the total for each dosing source for each subject in the LCIG group: LCIG morning dose, LCIG continuous infusion, LCIG extra dose, and LCIG overall. Each subject's average daily dose at each visit, overall and by dosing source, will be calculated by summing the total dose on each Subject Dosing Diary assigned to the visit and dividing by the number of diaries recorded. For LCIG subjects, only diaries reporting at least 12.8 hours of pump operation and only diaries after the initial LCIG titration will be included in this calculation.

For each scheduled visit the mean daily levodopa dose will be summarized, overall and by dosing source, with descriptive statistics (number of subjects with observations, mean, standard deviation, median, minimum and maximum values). The summaries for LCIG extra dose should only include the subjects who dosed in this manner at the visit.

For each scheduled visit during the Extension Period, the mean daily levodopa dose will be summarized, overall and by dosing source, with descriptive statistics (number of

subjects with observations, mean, standard deviation, median, minimum and maximum values) will also be provided for OMT/LCIG subjects who enter the Extension Period.

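### The levodopa-dose subgroup is measured after randomization and by a different rule in each arm, so its treatment-by-subgroup result is not a randomized comparison and can show an interaction that does not exist

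*SAP*

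**What the plan says.** SAP section 9.6 gives the aim of the subgroup analyses: "To determine if the following factors have an impact on the response to treatment". The outcome is change from baseline to final visit in NMSS and PDSS-2 total score. The model is an ANCOVA with treatment, country and subgroup as main effects, "treatment by subgroup interaction, and baseline score as the covariate". LS mean changes with 95% confidence intervals are reported for each stratum.

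One of the five factors is levodopa intake per day, below versus at or above 1250 mg, and its timing is given as "at the end of initial LCIG titration for the LCIG group and in the first set of dosing diary for the OMT group". The other four (gender, age, disease duration, and number of non-levodopa antiparkinsonian drugs in the week before randomization) are fixed before randomization and defined alike in both arms.

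Three other places bear on what the dose variable means:

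- **LCIG arm.** Protocol section 1.2 states that "those subjects randomized to LCIG must discontinue all other anti-PD medications" before LCIG starts. Protocol section 5.1.2.2 has the LCIG dose adjusted to each subject's optimal clinical response.
- **OMT arm.** Protocol section 5.1.2.1 asks that the regimen be kept stable. SAP section 8.6 places the diary after randomization: "Subjects in the OMT group are to record all anti-parkinsonian medications taken during the" treatment period.
- **Baseline dose.** For all randomized subjects, SAP section 8.6 takes the levodopa totals on the day before Visit 1 and "on the day of randomization will be considered the subject's screening and baseline levodopa dose", respectively.

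Section 9.6 does not use that baseline dose and attaches no caveat to the variable it does use.

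**The concern.** Asking whether a factor modifies the treatment effect requires a factor that treatment cannot change. Here the LCIG patients are sorted by a dose that exists only because of the assigned treatment and is set by how they respond to it. The OMT patients are sorted by a regimen that is meant to stay as it was. Patients in the same dose stratum are therefore not exchangeable between arms, and the benefit of randomization is lost within strata. This follows from the definition alone.

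There is also a gap in one arm only. SAP section 8.4 defines the first optimized prescription as the first pump settings unchanged for at least 7 days. Under that rule an LCIG patient who stops earlier has no titrated dose, yet enters the intent-to-treat dataset after a single dose (SAP section 5.0) and may have a final-visit score. Section 9.6 does not say how to classify that patient.

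What is at stake is the reading of the stratum results. A table of LCIG effect by levodopa dose invites a statement about which patients benefit more, and that statement could be an artefact.

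**Working it through.** **Inputs from the documents (SAP section 4.3).** NMSS improvement is 24.8 on LCIG and 8.2 on OMT, with SD 24, so the planned difference is 24.8 − 8.2 = 16.6. PDSS-2 improvement is 13.1 and 4.3, with SD 12.2, so the difference is 8.8. There are 44 patients per arm with 10% giving no post-randomization assessment: 44 × 0.9 ≈ 40 evaluable per arm.

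**The plan's own figure.** The documents give no number for the subgroup analysis. Their stated power for at least one endpoint (Hochberg, correlation 0.5 between endpoints) is 90%. Simulation gives 90.6% with 37 per group, and 90.7% with 44 per group and 10% baseline carried forward. The planning inputs therefore reproduce.

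**Closed form for the false interaction.** Suppose baseline dose does not modify the treatment effect, dose is normal and cut at its mean, and titrated dose has correlation r with outcome in the LCIG arm only. The mean of a standard normal above its centre is 0.798, so the two LCIG strata differ in mean outcome by

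2 × 0.798 × r × SD.

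Nothing offsets this in the OMT arm, so the whole amount appears as a difference in treatment effect between strata.

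| r (assumed) | NMSS, SD 24 | PDSS-2, SD 12.2 |
|---|---|---|
| 0.2 | 7.7 | 3.9 |
| 0.3 | 11.5 | 5.8 |
| 0.4 | 15.3 | 7.8 |
| Planned effect | 16.6 | 8.8 |

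A bivariate-normal simulation with 400,000 draws gave 7.5, 11.4 and 15.4 for NMSS.

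**The SAP's ANCOVA on simulated trials.** This used NMSS change with no true effect modification and 40 evaluable per arm. Assumptions not in the documents: baseline dose normal with mean 1250 mg and SD 450 mg, half the variance of titrated dose arising after randomization, all of the dose–outcome association running through that half, and 10 countries.

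| Dose used for the subgroup | Correlation with LCIG outcome | Mean false interaction (points) | Rejection at 5% |
|---|---|---|---|
| Titrated (LCIG), stable (OMT) | 0 | −0.1 | 5.1% |
| same | 0.14 | 5.4 | 7.6% |
| same | 0.28 | 10.7 | 15.1% |
| same | 0.42 | 16.2 | 29.7% |
| Baseline dose in both arms, not prognostic | – | 0.1 | 5.2% |
| Baseline dose in both arms, correlation 0.3 with outcome | – | −0.1 | 4.8% |

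The direction is not known in advance. In a separate run a correlation of −0.28 gave −11.0 points and 15.6% rejection.

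**A mean shift in dose.** With LCIG doses 200 mg higher on average, the rejection rates are 5.0%, 7.9%, 15.1% and 29.5% for the same four correlations, so a shift alone does not inflate the test. It does make the strata unlike: about 67% of LCIG patients but 50% of OMT patients fall at or above 1250 mg (69% and 50% if the dose SD is 400 mg).

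**The case against.** The strongest reply is that little depends on this analysis. It is one of five supportive factors, it lies outside the Hochberg and gatekeeping scheme of SAP section 9.5, and it uses final-visit change rather than the Week 26 MMRM contrast of section 9.2. The stated output is stratum LS means and intervals, with no planned interaction P value or dose-specific claim. All of that is correct, and it limits the consequence.

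The size can also be challenged:

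- The closed form turns an assumed correlation into points, and the documents give no such correlation. Titration aims at motor On and Off time, whereas blinded central raters score NMSS and PDSS-2, so the association could be weak.
- Protocol section 5.5.1.2 bases the starting LCIG dose on prior oral levodopa. Any LCIG-only association running through that component would be genuine modification by baseline dose. The ANCOVA simulation excludes this by construction, but its top case then needs a correlation of 0.6 with the post-randomization half of the dose (0.6 × 0.707 = 0.42), which is an upper-end scenario.
- With about 20 patients per cell, the interaction standard error is roughly 24 × √(4/20) = 10.7 points, a 95% half-width of about 21. A bias of 5 to 8 points sits inside that noise.
- The OMT first-diary dose approximates baseline, so the distortion comes almost entirely from the LCIG side.

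These points make the magnitude conditional. They do not make the factor a pre-treatment one or give it the same meaning in both arms.

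**Conclusion.** The concern holds. That the subgroup is post-randomization and arm-specific is plain from the text, so the stratum contrasts are not randomized comparisons whatever numbers are assumed. How misleading they would be is uncertain. With no association between titrated dose and LCIG outcome, the interaction test keeps its 5% level. With correlations of 0.14 to 0.42, the false NMSS interaction is about 5 to 16 points and the rejection rate 7.6% to 29.7%. The upper end is close to the whole planned effect. An association is plausible because response sets the dose, but its strength and sign are assumptions, as are the dose mean, SD and shift. The primary and key secondary conclusions are not touched. The definition should be changed because the analysis as written cannot answer the question the SAP sets for it.

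**What to change.** In SAP section 9.6, define this factor as total daily levodopa dose on the day of randomization, as derived in section 8.6, with the same 1250 mg cut in both arms. This makes it a pre-treatment factor like the other four, and patients who stop LCIG before completing titration are classified in the same way as everyone else. If titrated dose is of interest, present it only as a description within the LCIG arm; SAP section 8.5 already summarizes the prescribed dose at the first optimized prescription.

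The cost is one line of the SAP, with no new data and no new derivation. The one drawback is that 1250 mg may split baseline doses less evenly than titrated doses.

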10.0 Safety Analysis

10.1 General Considerations

Unless noted otherwise, all safety analyses will be performed on the Safety Dataset. Treatment group differences in safety parameters are evaluated using two-sided test at the significance of 0.050.

Unless otherwise specified, treatment group differences in continuous safety variables (e.g., changes from baseline to final observation on laboratory test variables) will be

assessed using an ANOVA model with the term of treatment, and the treatment group differences in binary safety variables will be evaluated using a Fisher's exact test.

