8.1.4 Safety Analysis

All safety analysis will be performed on the safety dataset unless otherwise specified. Comparisons between LCIG and OMT groups will be performed with two-sided test at the significance level of 0.05.

Unless otherwise specified, the treatment group differences in continuous safety variables (e.g., change from baseline to final observation on laboratory tests) will be assessed using an ANOVA model with the term of treatment, and the treatment group differences in binary safety variables will be evaluated using a Fisher's exact test.

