4.3 Sample Size

Approximately 88 subjects will be enrolled into the study and randomized in a 1:1 ratio to either optimized medical treatment or LCIG. There are no data on NMSS or PDSS-2 available from randomized trials comparing LCIG and OMT. Interim data from ongoing Phase 3b Study M12-920 showed that the improvement in NMSS total score from baseline to Week 12 is 24.8 in the LCIG group with standard deviation of 24. Results from Zibetti et al (2013) showed that the improvement in PDSS 2 total score after an average of 3.5 months of LCIG treatment was 13.1. The standard deviation was not provided and is estimated to be 12.2 assuming the correlation between baseline and follow-up visits is 0.5.

The significance level for this study is 0.05. For sample size determination, it is assumed that the improvement in the OMT group is 33% of the LCIG group, i.e., the improvement is 8.2 on NMSS total score and 4.3 on PDSS-2 total score, and that the correlation between these 2 measures is 0.5. Simulation showed that a study with 37 subjects per

group will have 90% power to declare statistical significance on at least one of these 2 alternative primary endpoints after multiplicity adjustment using Hochberg procedure. It is further assumed that 10% of randomized subjects in either treatment group will not provide post-randomization efficacy assessment. Additional simulations showed that 44 subjects per group will provide 90% power in the sensitivity analysis using baseline observation carried forward for subjects without post-randomization assessment. Therefore the total planned enrollment is decided to be 88 subjects.

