6.3 Definition of Baseline and Final Observation

Baseline for efficacy, health outcome and safety measures during the 26-week randomized treatment period will be defined as the last non-missing observation that is on or before the day of randomization.

Baseline for safety assessment during the Extension Period is defined as the last non-missing observation that is on or before the day of NJ/PEG-J placement for OMT subjects who enter the Extension Period. For LCIG subjects who enter the Extension Period, baseline of 26-week randomized treatment period will be used as the baseline of Extension Period.

The final visit for efficacy and health outcome measure will be defined as the last non-missing observation that is after the day of randomization for the OMT group during the 26-week randomized treatment period. The final visit for efficacy and health outcome measures for the LCIG group will be defined as the last non-missing observation that is after the date of the first LCIG infusion following PEG-J placement and no more than 1 day after the last LCIG infusion during the 26-week randomized treatment period.

The final observation for safety assessment during the 26-week randomized Treatment Period is defined as:

- For subjects in the OMT group and LCIG subjects who enter the Extension/Transition Period: the last non-missing observation that is after the day of randomization (for the OMT group) or after the initial device placement (for the LCIG group) and during the 26-week randomized treatment period.
- For LCIG subjects who do not enter the Extension/Transition Period: the last non-missing observation that is after the date and time of the first LCIG tube (NJ or PEG-J) placement procedure and no more than 1 day after the final removal of all LCIG tubes during the 26-week randomized treatment period.

The final observation for safety assessment during the Extension/Transition Period is defined as last non-missing observation for OMT/LCIG subjects who enter the Extension/Transition period.

Safety assessments on the date of the initial device placement procedure that do not have a time of assessment or sample collection recorded will be assumed to be post-procedure.

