9.3 Additional Efficacy Analyses

Secondary Analysis of the Primary Efficacy Variables

Analysis of covariance (ANCOVA) analyses will be carried out on change from baseline to final NMSS total score and change from baseline to final PDSS-2 total score. The ANCOVA model will contain treatment and country as the main effects and baseline score as the covariate. Sensitivity analyses will be carried out on the above variables with the same ANCOVA model using all randomized subjects. In this analysis, Baseline

Observation Carried Forward (BLOCF) will be applied to subjects who do not have post-randomization assessment of NMSS or PDSS-2.

Analysis of Secondary Efficacy Variables

The MMRM model, and the descriptive statistic summary described for the NMSS and PDSS-2 total score will also be used to evaluate the change from baseline in each of the following efficacy endpoints:

- UPDRS Part II score
- Parkinson's Disease Questionnaire-8 (PDQ-8) summary index
- NMSS domain scores
- PDSS-2 domain scores
- UPDRS total score, Part I score, Part III score, Part IV score
- Parkinson Anxiety Scale (PAS) total and subscale scores
- Geriatric Depression Scale (GDS-15)
- King's PD Pain Scale total and domain scores

For CGI-C and PGIC, an analysis of variance (ANOVA) model containing treatment and country as the main effects will be carried out.

UPDRS Part II score, CGI-C score and PDQ-8 summary index are key secondary endpoints. If both primary efficacy variables are statistically significant after adjusting for multiplicity, the Stepwise Gatekeeping Procedure will be utilized and the 3 key secondary endpoints will be tested using the Hochberg procedure with significance level of 0.05. Specifically, the following steps will be followed:

- If the largest of the 3 P values is ≤ 0.05 (i.e., all 3 P values are ≤ 0.05), all 3 key secondary endpoints are considered statistically significant.
- If the largest of the 3 P value is > 0.05 , then compare the middle P value with 0.025. The second and third key secondary endpoints are both statistically significant if the middle P value is ≤ 0.025 .

- If the largest of the 3 P value is > 0.05 and the middle P value is > 0.025 , then compare the smallest P value with 0.0167. If the smallest P value is ≤ 0.0167 , then the third key secondary endpoint is statistically significant. Otherwise, none of the 3 key secondary endpoints can be considered statistically significant.

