10.3.1 Analysis of Mean Changes for Laboratory Tests

Analyses of mean change from baseline to each planned visit and to the minimum, maximum and final value during the 26-week randomized treatment period will be presented by treatment group for each continuous hematology, chemistry, urinalysis, and special laboratory variable.

For each change from baseline analysis, the following summary statistics for each treatment group will be presented: sample size, baseline mean, visit mean, and the mean, standard deviation, and median of the change from baseline. The baseline and visit means will be calculated for each visit for subjects who have both a baseline and visit value. The

mean changes for the LCIG group and for the OMT group during the 26-week randomized treatment period will be compared using an ANOVA with treatment as the factor. LS mean, standard error, 95% confidence interval and *P* value will be presented.

Analyses of mean change from the Extension/Transition Period baseline to each planned visit and to the minimum, maximum and final value during the Extension/Transition Period will be presented for each continuous hematology, chemistry, urinalysis, and special laboratory variable for OMT/LCIG subjects who enter the Extension/Transition Period.

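### The safety comparisons of change from baseline use a treatment-only ANOVA; the test is valid, but it gives up precision that the recorded baseline value would supply

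*SAP*

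**What the plan says.** SAP 10.1 sets the default for continuous safety variables: differences between arms are to be "assessed using an ANOVA model with the term of treatment". Protocol 8.1.4 says that they "will be assessed using an ANOVA model with the term of treatment". For laboratory tests, SAP 10.3.1 states that the mean changes in the two arms "will be compared using an ANOVA with treatment as the factor". SAP 10.4.1 (vital signs and weight) and 10.5.1 (ECG) use the same model. Each of these three sections reports LS means, standard errors, 95% confidence intervals and P values, and SAP 10.1 has the differences "evaluated using two-sided test at the significance of 0.050". No safety section adds a covariate.

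SAP 6.3 has one definition covering "Baseline for efficacy, health outcome and safety measures": the last non-missing value on or before the day of randomization. SAP 10.3.1, 10.4.1 and 10.5.1 calculate the baseline and visit means only in subjects who have both values.

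The efficacy side of the same plan is different. For NMSS and PDSS-2, the ANCOVA in SAP 9.3 "model will contain treatment and country as the main effects and baseline score as the covariate". The MMRM in 9.2 and the subgroup models in 9.6 also contain baseline and country. Protocol 8.3 stratifies randomization by country.

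**The concern.** The plan adjusts change scores for baseline when it studies benefit and does not when it studies safety, and it gives no reason for the difference. Subtracting the baseline does not make full use of it. Unless the regression slope of follow-up on baseline is 1, part of the between-subject baseline variation stays in the change score as noise. The covariate needs no new data and drops no subject.

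The cost falls on a trial of about 44 per arm, in comparisons that include body weight, vitamins B6 and B12, folic acid, methylmalonic acid and homocysteine. Intervals for these differences would be wider than necessary.

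**Working it through.** **The plan's own figures.** The documents state no power or precision for any safety comparison. The power that they do state is for efficacy, and it reproduces. With differences 24.8 − 8.2 = 16.6 (SD 24) and 13.1 − 4.3 = 8.8 (SD 12.2), correlation 0.5 between endpoints and the Hochberg rule, simulation gives 90.6% at 37 per group against the stated 90%. At 44 per group with 10% set to zero change it gives 90.9%. This does not bear on the safety models.

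**Inputs.** Group size: "Approximately 88 subjects will be enrolled into the study and randomized in a 1:1 ratio" (SAP 4.3), so 44 per arm. Correlation rho between baseline and follow-up: not given for labs, vital signs, weight or ECG; assumed 0.3 to 0.98. The 0.5 in SAP 4.3 is a planning assumption for PDSS-2 and is not evidence about safety variables.

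**Formulas.** Let s_B and s_F be the SDs at baseline and follow-up. Per-subject variances are:

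- change score: s_F² + s_B² − 2·rho·s_F·s_B
- baseline-adjusted: s_F²(1 − rho²)
- difference between the two: (s_B − rho·s_F)², which is never negative.

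With equal SDs (sigma), these become 2·sigma²(1 − rho) and sigma²(1 − rho²), so the ratio of adjusted to unadjusted variance is (1 + rho)/2.

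**Results at 44 per arm, equal SDs.** Simulated ratios (20,000 trials) fit the adjustment and so include the cost of estimating the baseline slope. The power column takes a difference that the ANOVA detects with 80% power; for example, at rho 0.5, 2.80/√0.75 − 1.96 = 1.27, giving 89.9%. The last column is 44 divided by the formula ratio.

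| Assumed rho | Ratio, formula | Ratio, simulated | 80% power becomes | ANOVA n per arm to match |
|---|---|---|---|---|
| 0.3 | 0.65 | 0.65 | 93.5% | 67.7 |
| 0.5 | 0.75 | 0.75 | 89.9% | 58.7 |
| 0.7 | 0.85 | 0.86 | 86.0% | 51.8 |
| 0.9 | 0.95 | 0.96 | 82.0% | 46.3 |
| 0.98 | 0.99 | 1.00 | 80.4% | 44.4 |

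At 40 per arm the simulated ratios are nearly the same (0.65, 0.76, 0.86, 0.96 and 1.00).

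**The equal-SD assumption.** With k = s_F/s_B the ratio is k²(1 − rho²)/(1 + k² − 2·rho·k). At rho 0.7:

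- k = 0.8: 0.3264/0.52 = 0.63
- k = 1: 0.51/0.60 = 0.85
- k = 1.2: 0.7344/0.76 = 0.97

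The values of k are illustrative. The size of the gain therefore depends on k as well as rho. Equal SDs are least likely for change to the minimum or maximum value, which the three sections also analyse.

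**Chance imbalance.** With equal SDs, a baseline difference d between arms shifts the ANOVA estimate by (rho − 1)·d. The SE of d is √(2/44) = 0.213 SD. A difference of 0.3 SD is 0.3/0.213 = 1.41 SE and is reached or exceeded, in either direction, in about 16% of draws. It shifts the estimate by 0.21, 0.15, 0.09 and 0.03 SD at rho 0.3, 0.5, 0.7 and 0.9. This is the variance gap again: at rho 0.5 the gap is (1 − 0.75) × 2/44 = 0.0114, and the variance of the shift is 0.5² × 2/44 = 0.0114.

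**The case against.** The strongest reply is that nothing here is an error. Averaged over randomizations, an ANOVA on change is unbiased and its type I error is correct. The protocol and SAP agree with each other. The planned tables put each arm's baseline mean beside its mean change, so a reader can see an imbalance. All of that stands.

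It also stands that the gain is small for stable variables. At a correlation of 0.9 the variance falls by about 5%, and near 0.98 the lost degree of freedom cancels it. Weight may be such a variable, although the documents do not say.

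Three stronger readings are tempting, and the documents do not support them:

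- A reader might count chance imbalance as a bias on top of the lost precision. The ANOVA standard error already contains it, as the variance identity shows.
- A reader might say that a change score over-corrects whenever the correlation is below 1. What matters is the slope, rho·s_F/s_B, which can reach or exceed 1 if the follow-up SD is larger.
- A reader might infer that detection of weight loss or polyneuropathy is compromised. SAP 10.2.3 identifies those adverse events of special interest by MedDRA queries. The BMI shift tables (10.4.2), the potentially clinically significant weight criterion (10.4.3, Appendix G) and the laboratory shift tables (10.3.2) do not use this model.

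The case for country is weaker than that for baseline. Its effect on precision is not quantified here, and it uses more degrees of freedom. The reason to include it is consistency with the stratified randomization and the efficacy ANCOVA. None of these points favours leaving baseline out.

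**Conclusion.** The point holds as an efficiency improvement to supportive safety comparisons. The planned test is valid; it is less precise than the collected data allow. Under equal SDs, adjustment removes 35%, 25%, 15% and 5% of the variance at assumed correlations of 0.3, 0.5, 0.7 and 0.9, and essentially nothing near 0.98. No safety correlation is available, so the gain for a particular variable cannot be fixed within that range, and unequal SDs would change it. The primary efficacy analysis does not use these models and is unaffected.

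**What to change.** In Protocol 8.1.4 and SAP 10.1, 10.3.1, 10.4.1 and 10.5.1, replace the treatment-only ANOVA for between-arm change from baseline with an ANCOVA. Use treatment as factor, the baseline value of the same variable as covariate, and country as in the efficacy ANCOVA. Report the adjusted LS mean difference with its 95% CI. The hourly post-infusion vital signs, shift tables and summaries of potentially clinically significant values have no between-arm test and need no change. SAP 12.0 states that the analyses do not depart from the protocol, so the two documents should change together, or SAP 12.0 should record the difference.

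The cost is wording, one model statement, and a check of linearity and influential values across the laboratory variables. Baseline uses one degree of freedom. Country uses about nine, with about 10 countries. With 88 subjects analysed, residual degrees of freedom fall from 88 − 2 = 86 to about 88 − 2 − 1 − 9 = 76. No new data are needed and no subject is lost.
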